### **5.10. Reduction of All-Cause Mortality**

All-cause mortality will be evaluated descriptively with Kaplan-Meier time-to-event methods. The event date will be the date of death. Living subjects will be censored at the date of last contact. The estimate of survival and corresponding 95% log-log confidence interval as well as the number of subjects at risk and number of subjects that die will be presented at 6 months, 12 months, 24 months, and annually thereafter. The hazard ratio between arms and its 95% confidence interval will be estimated by a proportional hazard's regression model.

### **5.11. Reduction of Heart Failure Mortality and Heart Failure Morbidity**

The morbidity and mortality endpoint will be repeated with a revised definition for the terminal events that contribute to the event count outcome in the analysis. Only mortality events where the cause of death is heart failure will be counted as death endpoint events. All other deaths are censoring events, but not counted as primary endpoint events. The LVAD, heart transplant and heart failure morbidity events are treated the same as the main primary analysis (i.e., included in the analysis as primary events).

### **5.12. Reduction of HF Mortality**

Mortality due to heart failure will be evaluated descriptively with Kaplan-Meier time-to-event methods. The event date will be the date of the heart failure death. Living subjects will be censored at the end of follow-up as defined in Section 2.1.1. Subjects that die due to non-heart failure causes will be censored at the date of death. The estimate of survival and corresponding 95% log-log confidence interval as well as the number of subjects at risk and number of subjects that die will be presented at 6 months, 12

months, 24 months, and annually thereafter. The hazard ratio between arms and its 95% confidence interval will be estimated by Cox proportional hazards regression.

### **5.13. Reduction in the Rate of within 30-day re-hospitalization for Heart Failure**

Incidence of re-hospitalization for heart failure within 30-days by treatment arm will be analyzed descriptively.

### **5.14. Additional Mortality and Heart Failure Morbidity Definitions**

Additional definitions of morbidity and mortality events will be explored as sensitivity analyses. These sensitivity analyses include pre-defined heart failure definitions that vary in severity and intensity of symptoms and/or heart failure treatments. These definitions may reflect recent changes and approaches to the care of heart failure patients.

## **6. ANCILLARY ENDPOINTS**

The following endpoints will be evaluated for exploratory and supportive purposes. No formal hypotheses are provided.

### **6.1. New York Heart Functional Class (NYHA)**

NYHA Class will be collected at baseline, 6, 12, 18 and 24 months. The frequency and percentage of subjects who improved in NYHA Class from baseline at each follow-up time point by treatment arm will be presented. A generalized estimating equation (GEE) repeated measures logistic model with a compound symmetry working correlation will be used to account for within subject correlation over time and to estimate the odds ratio for improved NYHA Class between the randomized arms over all times at which the endpoint is collected adjusted for baseline.

### **6.2. Minnesota Living With Heart Failure (MLWHF)**

MLWHF questionnaire is collected at baseline and at 6, 12, 18 and 24 months. The mean improvement in MLWHF between baseline and at each follow-up time point by treatment arm will be presented with means and confidence intervals. A generalized estimating equation (GEE) repeated measures model with a compound symmetry working correlation will be used to account for within subject correlation over time and to estimate the difference between the randomized arms over all times at which the endpoint is collected adjusted for baseline.

### **6.3. EuroQol 5-Dimension (EQ-5D)**

EQ-5D questionnaire is collected at baseline and at 6, 12, 18 and 24 months. Changes from baseline will be calculated at each follow-up time point for the index score and visual analogue score within each treatment arm. The mean improvement in EQ-5D between baseline and at each follow-up time point by treatment arm will be presented

with means and confidence intervals. A generalized estimating equation (GEE) repeated measures model with a compound symmetry working correlation will be used to account for within subject correlation over time and to estimate the difference between the randomized arms over all times at which the endpoint is collected adjusted for baseline.

#### **6.4. Procedure Related Complications - Implant and 30 days Post-implant**

Incidence of procedure related complications occurring between implant and 30 days post-implant will be analyzed descriptively with frequency counts and percentages for the safety population. The numerator will include the number of subjects with at least one procedure related complication occurring between implant and 30 days post-implant. The denominator will include subjects who have had an implant, or an implant attempted.

#### **6.5. System Related Complications – 30 day to 6 months Post-implant**

Incidence of system related complications occurring between 30 days and 6 months post-implant will be analyzed descriptively with frequency counts and percentages for the safety population. The numerator will include the number of subjects with at least one system related complication occurring between 30 days and 6 months post-implant. The denominator will include subjects who have had an implant, or an implant attempted.

## 7. COVID-19

On March 13, 2020, the US announced a national emergency declaration due to the COVID-19 pandemic. Due to the changes in care patterns and accessibility to healthcare, as well as the interruption of logistics at trial sites, COVID-19 has had a significant impact on the execution, results and interpretation of clinical trials. These issues have been discussed globally by medical groups as well as governmental agencies. In addition, there are examples from recent clinical trial that have demonstrated the potential impact of COVID-19 on the effectiveness of therapies.

To adjust for, measure and understand the impact of COVID-19, several changes, including the collection of key data, were prospectively made to the trial in early 2020, including:

- Completion of randomizations at a total of 467 subjects randomized (13 less than then 480 randomized originally planned).
- To minimize the exposure of subjects, site personnel and CVRx personnel to COVID-19, protocol required follow-up visits could be completed via telephone. This reduced or delayed the completion of testing required at certain follow-up visits (e.g., six minute hall walks, blood draws). These deviations were specifically collected and noted as related to COVID-19.
- All site monitoring is done remotely until the site, CVRx and the monitor agree that an in-person meeting is safe and necessary.
- Device programming, if possible and appropriate, may be done remotely.
- A COVID-19 case report form (see Section 8 for copy of form), dedicated to understanding the impact of COVID-19 on subjects in the trial, was designed and implemented based on a template developed by the Heart Failure Collaboratory ([www.hfcollaboratory.com](http://www.hfcollaboratory.com)). This form is required for all subjects for all follow-up visits starting on or after 01April2020, depending on IRB approval and/or site implementation. The form includes questions such as: “Since the last visit did the subject FEEL THE NEED to go to an emergency department or hospital for their heart failure BUT DECIDED NOT TO because of concerns about COVID-19”.
- The CEC Charter was updated to collect COVID-19 relatedness to endpoint. Specifically, for each adjudicated event the following evaluation of the impact of COVID was documented:
  - If COVID-19 is the primary reason for hospitalization, the committee indicates a secondary reason for hospitalization.
  - If COVID-19 is not the primary reason for hospitalization, the committee indicates whether it was a contributing factor.
  - If a determination cannot be made regarding the primary reason, the committee marks both as the primary reason.

Despite, or possibly because of, these changes, the impact of COVID-19 on the overall Barostim Therapy (BAT) treatment effect in this trial is unknown. Therefore, the following approach has been outlined to evaluate and measure any potential impact on the M&M endpoint. Sixty percent (60%) of the approximate 320 expected primary events occurred prior

to March 13, 2020. Thus, approximately 40% of the expected events will accrue during the COVID pandemic. This section outlines additional analyses of the M&M endpoints that may be conducted, as well as the qualitative summaries that will be provided in the assessment of the impact of the COVID-19 pandemic on the M&M data and conclusions.

To evaluate the impact of COVID-19 on the morbidity and mortality endpoints, an indicator variable reflecting events pre vs post the March 13, 2020 date will be included in the regression model and evaluated using a treatment-by-COVID-19 interaction. A p-value less than 0.15 for the interaction term will be considered evidence of a significant interaction between the treatment effect pre COVID-19 vs post COVID-19 (consistent with the interaction p-value for site and gender defined in the main Statistical Analysis Plan 360050-001). However, an insignificant interaction p-value ( $p \geq 0.15$ ) does not necessarily mean that there is no significant difference in the magnitude of the benefit from Barostim therapy pre vs post COVID-19, primarily due to potentially low statistical power for evaluating the interaction term. Thus, the interaction p-value will be included as part of the totality of information used to characterize and evaluate the potential impact of COVID-19.

A stratified analysis, using the negative binomial model as specified in the primary analysis, may also be performed to further evaluate any difference in treatment effect pre-March 13, 2020, versus post-March 13, 2020. Separate estimates of the treatment effect will be made with data pre-March 13, 2020, and post-March 13, 2020. The follow-up time for the first model will be censored on March 12, 2020, while the follow-up start time for the second model will be March 13, 2020. The Anderson-Gill method for recurrent events model may also be used along with a time-varying covariate for follow-up pre- and post- March 13, 2020. The significance of the time-varying covariate as well as the interaction with treatment group would be reported. As with the negative binomial model, a p-value for the interaction term less than 0.15 will be considered evidence of a significant interaction between the treatment effect pre COVID-19 vs post COVID-19.

If there is evidence that the treatment effect is different pre- vs post-March 13, 2020, then the benefit observed pre-March 13, 2020 would be more consistent with the assumptions and definitions of the study endpoints. This includes the definition and assumed event rate for heart failure hospitalization, as it has been observed that patients have shown a reluctance to interact with the health care setting during the COVID-19 pandemic, some by reducing their risk of hospitalization by changing their behaviors and others by receiving care remotely to replace what may have previously been a hospitalization (e.g. acute medication changes).

In addition to the analyses specified above, other additional relevant information will be considered, such as:

- Number and percent of pre- vs post- March 2020 information (events, follow-up time, rate)
- Follow-up visit compliance pre- vs post- March 2020
- Comparison of other definitions of heart failure on event rates between treatment arms pre- vs post- March 2020, such as
  - Expanded definition of heart failure (see CEC Charter)
  - Unscheduled clinic visits

- Acute changes in medications
- Evaluate the impact using the responses on the COVID-19 case report form. This includes summarizing, or incorporating in the analyses, the instances where subjects reported the need to go to an emergency department or hospital for their heart failure but decided not to because of concerns about COVID-19.
- Evaluate the information regarding the CEC determined impact of COVID-19 on events, such as HF hospitalizations where CEC determined the event was a study endpoint, but COVID-19 was considered a “Co-primary” or a contributing factor, or where COVID-19 was the primary reason for hospitalization, but heart failure was the secondary reason.
- Evaluate all COVID related adverse events and deaths
- Evaluate COVID related deviation and the impact on the trial and results

There are three interim analyses schedule at approximately 140 (44%, Jan 2020), 180 (~56%, Oct 2020), 240 (~75%, Oct 2021) primary endpoint events, and a final at ~320 events (100%, TBD). Thus, the first and possibly much of the second interim analyses primarily include data that were not impacted by COVID-19. As such, these analyses may also provide insight into the impact of COVID-19 and will be provided in the PMA Supplement submission.

The totality of evidence available will be considered when evaluating the impact of COVID. This includes all evidence of a differential treatment effect of Barostim therapy pre- vs. post-March 13. This includes, at a minimum, the analyses specified above as well as the qualitative assessments of the impact of the COVID-19 pandemic on the study based on the relevant information collected above.

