## 5.2. M&M endpoints with follow-up ending at 6, 12 and 24 months

Over the course of follow-up in the trial, there were many unexpected changes that occurred in patient care that could confound the evaluation of the benefit of Barostim therapy. These include the approval and adoption of pharmaceutical and device-based treatments for heart failure (e.g., ARNI, SGLT2, Cardiac Contractility Modulation), as well as changes in care patterns and practices due to COVID-19. To better understand the impact of these event, the analyses on the morbidity and mortality endpoints will be repeated assuming that follow-up stops at 6 months, 12 months and 24 months. The same endpoint definitions as described above and analysis methods in Section 2.1.4 will be repeated while censoring follow-up time and events at 6, 12, and 24 months.

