3. Type I error calculated assuming an expected relative reduction in the endpoint event rate of  $1 - \exp(\beta_1) = 0$ , equivalent to no treatment effect
4. Statistical significance threshold given by the Hwang-Shih-DeCani spending function with  $\gamma = -3$

5. Sample size of 331 subjects with baseline NT-proBNP < 1600, consisting of 259 subgroup subjects randomized through 03October2018 and an additional 72 subjects to be prospectively randomized.
6. Parameter describing the relationship between events in the year prior to randomization and the expected rate of events during follow-up (beta) of 1.8
7. Parameter describing the probability that an event is a censoring event (p) of 0.18
8. Parameter describing the dispersion of the negative binomial data (alpha) of 1.7

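### The pre-/post-13 March 2020 comparison in SAP Section 7 is substantially confounded with time since implant, so a fading device effect could be taken for a COVID-19 effect

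*SAP*

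**What the plan says.** SAP Section 7 sets out how a pandemic effect on the morbidity and mortality endpoint will be examined.

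- For the main test, "an indicator variable reflecting events pre vs post the March 13, 2020 date will be included in the regression model" and is crossed with treatment. "A p-value less than 0.15 for the interaction term will be considered evidence of a significant interaction".
- Separate negative binomial fits for the two periods are optional. The first is censored on 12 March 2020, and "the follow-up start time for the second model will be March 13, 2020". An Andersen-Gill model with period as a time-varying covariate is also optional.
- If the effects differ, "then the benefit observed pre-March 13, 2020 would be more consistent with the assumptions and definitions of the study endpoints".
- A non-significant interaction is not to be taken as showing no difference, and the p-value is one item in an overall weighing of evidence.

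The models elsewhere in the SAP do not add time since implant as a modifier of the treatment effect. The primary model (Section 3.1.4) contains treatment and prior heart failure hospitalizations. Section 5.3 adds Andersen-Gill and joint frailty models with no time-varying treatment effect. Under Section 5.2 "the analyses on the morbidity and mortality endpoints will be repeated assuming that follow-up stops at 6 months, 12 months and 24 months", and that section presents the exercise as a way to study changes in care and COVID-19.

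On enrolment, Section 8.1 counts "259 subgroup subjects randomized through 03October2018". Section 1 adds 59 more, the last on 29 July 2020.

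**The concern.** Most subjects had been in the trial for well over a year by 13 March 2020, so the post-cut period is largely late follow-up. If the device's benefit weakened with time since implant and the pandemic had no influence on it, the treatment effect would still look smaller after the cut. Randomization does not prevent this, because both arms age together and fading appears directly as a treatment-by-period interaction.

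Section 7 does not mention fading as an alternative explanation, and its one interpretive sentence points towards the pre-cut estimate. Durability is a property of a permanent implant, and these analyses are meant to support a PMA supplement. A loss of benefit over time could be presented as a pandemic artefact and the more favourable early figure put forward.

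**Working it through.** **The plan's own figures.** The SAP says that "Sixty percent (60%) of the approximate 320 expected primary events occurred prior" to 13 March 2020: 0.60 × 320 = 192. No event dates are given, so this cannot be checked. The interim schedule, "140 (44%, Jan 2020), 180 (~56%, Oct 2020), 240 (~75%, Oct 2021) primary endpoint events", has correct percentages (140/320 = 44%, 180/320 = 56%, 240/320 = 75%). However, 192 events before March 2020 fits 180 events in October 2020 only if the schedule shows adjudication or analysis dates. The SAP should say which.

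**Inputs from the documents**
- 259 subjects randomized by 3 October 2018 and 59 later. 259 + 59 = 318; 331 − 13 also gives 318, while SAP Section 1 states 319.
- Time zero is the actual or anticipated implant date (SAP 3.1.5). Implant is due within 14 days of randomization, or 28 with a proctor (Protocol Table 6).
- Control rate 0.4 per patient-year, rate ratio 0.65, terminal fraction 0.18, and dispersion 1.7 (SAP 8.1). The dispersion is read as a gamma shape, because SAP Table 4 labels 1.4 as large overdispersion.

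**Step 1: dates.** From 3 October 2018 to 13 March 2020 is 527 days, or 527/30.44 = 17.3 months. After a 14-day lag it is 513/30.44 = 16.9 months, and after 28 days 499/30.44 = 16.4 months. So for 259/318 = 81% of subjects, any post-cut time lies beyond about 16–17 months. SAP Table 2 shows that 18 of the 259 contribute interim data only. Among those with possible later follow-up the share is 241/(241 + 59) = 80%.

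**Step 2: person-time.** The documents do not give the accrual pattern, exit rate or end of follow-up. The main assumptions were: accrual starting between February 2015 and February 2017, uniform or accelerating; the later 59 spread to 29 July 2020; follow-up ending June or December 2022; and exit hazard 0.072–0.15 per year. Including runs under other assumptions:
- post-cut time beyond 18 months: 87–92%
- pre-cut time already beyond 18 months: 23–48%
- share of all time beyond 18 months that is pre-cut: 17–45%
- correlation of period with time since implant: 0.59–0.74 (0.44–0.70 with the 18-month split)

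**Step 3: simulation.** 1,500 trials per scenario; three accrual patterns (starting October 2015, July 2016 or February 2017); follow-up to December 2022; exit hazard 0.15; gamma frailty of shape 1.7. The control rate was set to give about 320 events (0.30–0.37 per year). The analysis was a Poisson rate model with subject-clustered standard errors. The interaction was tested at two-sided p<0.15, without and then with treatment × (>18 months).

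| Truth (rate ratio) | Flagged, planned form | Flagged, with added term | Median post/pre ratio, planned → adjusted |
|---|---|---|---|
| Constant 0.65 | 14–17% | 16–19% | 1.00–1.01 → 0.99–1.02 |
| 0.65 → 1.0 at 18 months, no COVID effect | 30–41% | 14–18% | 1.22–1.33 → 0.98–1.00 |
| 0.50 → 1.0 at 18 months, no COVID effect | 43–69% | 15–18% | 1.34–1.58 → 0.98–1.01 |
| 0.65 → 1.0 at 13 March 2020, no fading | 66–67% | 44–57% | 1.54–1.57 → 1.54–1.57 |

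In the second row the fitted rate ratios are 0.73–0.79 before the cut and 0.96–0.97 after it; in the third, 0.61–0.70 and 0.94–0.96. Nearly all flags in these two rows favour the pre-cut period.

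A second set-up used the SAP's rate of 0.4, terminal events, 4% per year withdrawal, the 259 entries spread over the 2.4 years before 3 October 2018, and a negative binomial fit. With 0.55 fading to 0.95 it gave a flag favouring the pre-cut period in 42% of trials, against 7% in that direction under a constant effect.

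**Step 4: cost of the added term.** The interaction standard error rises from about 0.24 to 0.27–0.33 across these rows (0.27/0.24 = 1.13; 0.33/0.24 = 1.38). The overlap in Step 2 predicts much the same: √[1/(1 − 0.44²)] = 1.11 and √[1/(1 − 0.70²)] = 1.40. In further runs, power for a true COVID-19 effect fell from 71% to 60% and from 62% to 52%.

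**The case against.** The strongest reply is that Section 7 does not rest on the interaction alone. It collects evidence specific to the pandemic: reports on the COVID form of hospital or emergency visits avoided, unscheduled clinic visits, acute medication changes, and the events committee's view of COVID-19 relatedness. Simple fading would not generate avoided-care reports. This stands, and a reader should not infer that the SAP attributes every pre/post difference to COVID-19. But those data show whether the pandemic affected care. They do not show whether the device effect weakened with time.

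Secondly, Section 5.2 gives some information. Under the second set-up's accrual, about 83% of person-time in months 0–24 and 70% in months 18–24 precedes the cut, so a drop between the 12- and 24-month estimates would be mainly pre-pandemic evidence of fading. That helps, but only six months of follow-up beyond month 18 enter it, and no formal contrast between truncation points is planned. The annual Kaplan-Meier estimates (Sections 5.9 and 5.10) help in the same limited way. The early interim looks, offered as insight into COVID-19, also have shorter follow-up and so share the confounding.

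Thirdly, the size depends on undocumented inputs, and the 18-month step was chosen close to the 17.3-month gap. The simulated share of events before the cut is 40–55%, below the SAP's 60%. The accrual pattern nearest to 60% gives the lower end of the flagging ranges (30% and 43%). This stands as a caution about size.

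**Conclusion.** The concern holds as substantial, partial confounding. Post-cut follow-up is about nine-tenths late follow-up, no planned model separates period from time since implant, and fading alone raises the chance of a flagged interaction from about 15% to 30–42%, or to 43–69% if a 50% reduction is lost entirely. These figures rest on the assumed accrual start, exit rate, end of follow-up, an abrupt change at 18 months and a two-sided reading of p<0.15.

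Three stronger readings are not supported. Period and time since implant are not the same variable: staggered entry leaves 23–48% of pre-cut time beyond 18 months, which is why the extra term can be estimated. Fading would not necessarily be read as COVID-19: even complete loss of the planned 35% reduction goes unflagged in most simulated trials. And the primary result is not compromised: it pools all follow-up, Section 3.2 leaves it unchanged, and fading already dilutes it. What is at risk is the interpretation of the late data and the labeling argument.

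**What to change.** 1. In the Section 7 models, divide each subject's follow-up at 13 March 2020 and by time since implant (for example at 18 months, fixed in advance), and add time since implant and its interaction with treatment. Use subject-clustered standard errors.
2. Report this model beside the planned unadjusted one, with both interactions. Present the treatment-by-time-since-implant result as the durability finding.
3. Amend the sentence that favours the pre-March 2020 benefit. It should say that a pre/post difference may reflect loss of effect over time as well as COVID-19, and that the pre-cut estimate is to be interpreted in light of both models.

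The adjusted test should not become a strict precondition for calling a difference COVID-related. Its standard error is about 13–38% larger, and power for a true COVID-19 effect falls from about 62–71% to 44–60%. The SAP already warns that interaction power may be low, so both results should be shown. Otherwise the change needs only SAP wording and extra model terms, using dates already collected. It should be settled before the arms are compared; if added afterwards, it should be labelled post hoc.
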